7.8. Imaging

MRI or CT scan with contrast will be performed at screening if not performed previously. Results must be available and reviewed as soon as possible and before the subject is randomized.

[figure not shown]
Note: in the event that a CT or MRI scan is needed, it must be performed as soon as possible after Visit 1 if it cannot be performed on the day of that visit.

CCI

[figure not shown]
CCI

090177e18f46d803\Approved\Approved On: 31-Aug-2018 06:42 (GMT)

CCI

CCI

8. ADVERSE EVENT REPORTING

8.1. Adverse Events

All observed or volunteered adverse events regardless of treatment group or suspected causal relationship to the investigational product(s) will be reported as described in the following sections.

For all adverse events, the investigator must pursue and obtain information adequate both to determine the outcome of the adverse event and to assess whether it meets the criteria for classification as a serious adverse event requiring immediate notification to Pfizer or its designated representative. For all adverse events, sufficient information should be obtained by the investigator to determine the causality of the adverse event. The investigator is required to assess causality. Follow-up by the investigator may be required until the event or its sequelae resolve or stabilize at a level acceptable to the investigator, and Pfizer concurs with that assessment.

As part of ongoing safety reviews conducted by the Sponsor, any non-serious adverse event that is determined by the Sponsor to be serious will be reported by the Sponsor as an SAE. To assist in the determination of case seriousness further information may be requested from the investigator to provide clarity and understanding of the event in the context of the clinical trial.

8.2. Reporting Period

For serious adverse events, the active reporting period to Pfizer or its designated representative begins from the time that the subject provides informed consent, which is obtained prior to the subject's participation in the study, ie, prior to undergoing any study-related procedure and/or receiving investigational product, through and including 28 calendar days after the last administration of the investigational product. Serious adverse events occurring to a subject after the active reporting period has ended should be reported to the Sponsor if the investigator becomes aware of them; at a minimum, all serious adverse events that the investigator believes have at least a reasonable possibility of being related to study drug are to be reported to the Sponsor.

- AEs (serious and non-serious) should be recorded on the CRF from the time the subject has taken at least one dose of study treatment through last subject visit.

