6.1.1. Visit 2 Baseline Video-EEG (Day -3 to -1)

The following activities will be performed at Visit 2, which is scheduled to assess partial onset seizure frequency by Video-EEG monitoring as an inpatient.

- Placement of EEG electrodes and recording device and instruction of parent(s)/guardian(s)/caregiver(s) of its usage.
- Dispense seizure event log to track observed seizure events during Video-EEG and train parent(s)/guardian(s)/caregiver(s) on its use and completion.
- Record all concomitant medications and non-drug treatments and procedures, including any ongoing AED's.
- Assess and record adverse events.

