6.2. Double-Blind Dose Escalation Phase

6.2.1. Visit 3 (Day 1 \pm 1) Randomization and Entry into Double-blind Dose Escalation Phase

Randomization: Subjects who satisfy all of the eligibility criteria at this study visit may be randomized and will receive the initial dose of study medication at the clinic during this visit.

The following activities will be performed at Visit 3:

- Verify conformance with entry criteria by reviewing inclusion/exclusion criteria.
- Verify the criteria for total number of qualifying seizures has been met by review of the Video-EEG by the investigator/or designee.
- Record all concomitant medications and non-drug treatments and procedures, including any ongoing AED's.
- Record weight and height/length.
- Assess and record adverse events.
- Perform brief physical examination which includes recording vital signs including blood pressure and pulse.

- Perform brief neurological examination.
- Collect blood and urine specimens for clinical laboratory assessments. If it is not feasible to obtain a urine sample, then no urine sample will be required.
- Assign randomization number and dispense blinded study medication via tele-randomization system.
- Train parent(s)/guardian(s)/caregiver(s) on study medication dosing and administration and demonstrate use of oral syringe/bottles. Have parent(s)/guardian(s)/caregiver(s) practice dosing in office to verify comprehension of dosing instructions.
- Administer first dose of study medication in clinic.
- Dispense daily dosing diary.
- Download Video-EEG recording data.
- Transmit Video-EEG data to central reader for assessment.
- Collect seizure event log and send to central reader.

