7.6. Physical and Neurological Examination

A physical examination will be performed and must be completed by a Medical Doctor (MD), Doctor of Osteopathy (DO), Nurse Practitioner (NP) or Physician Assistant (PA) or appropriate equivalent based upon normative country specific practices.

Full physical and neurological exams will be performed at Visit 1 and Visit 7 (ie, at the completion of the study or early termination). A brief physical exam and neurological exam documenting significant changes from the baseline exam will be performed at Visit 3.

Physical examinations will evaluate the following body systems/organs: general appearance; dermatological; head and eyes; ears, nose, mouth, and throat; pulmonary; cardiovascular; abdominal; genitourinary (optional); lymphatic; musculoskeletal/extremities; and neurological.

Any clinically significant changes from the entry examination will be recorded as adverse events and the specific finding(s) documented with an Investigator Comment.

Neurological exam will assess: level of consciousness, mental status, cranial nerve assessment, muscle strength and tone, reflexes, pin prick and vibratory sensation (the latter using a 128-Hz tuning fork), coordination and gait.

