8.8. Causality Assessment

The investigator's assessment of causality must be provided for all adverse events (serious and non-serious); the investigator must record the causal relationship in the CRF, as appropriate, and report such an assessment in accordance with the serious adverse reporting requirements if applicable. An investigator's causality assessment is the determination of whether there exists a reasonable possibility that the investigational product caused or contributed to an adverse event; generally the facts (evidence) or arguments to suggest a causal relationship should be provided. If the investigator does not know whether or not the investigational product caused the event, then the event will be handled as "related to investigational product" for reporting purposes, as defined by the Sponsor (see section on Reporting Requirements). If the investigator's causality assessment is "unknown but not related to investigational product", this should be clearly documented on study records.

In addition, if the investigator determines a serious adverse event is associated with study procedures, the investigator must record this causal relationship in the source documents and CRF, as appropriate, and report such an assessment in accordance with the serious adverse event reporting requirements, if applicable.

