8.11.2. Non-Serious Adverse Event Reporting Requirements

All adverse events will be reported on the adverse event page(s) of the CRF. It should be noted that the form for collection of serious adverse event information is not the same as the adverse event CRF. Where the same data are collected, the forms must be completed in a consistent manner. For example, the same adverse event term should be used on both forms. Adverse events should be reported using concise medical terminology on the CRFs as well as on the form for collection of serious adverse event information.

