6.2.1. Adverse Events

All AEs occurring during the course of the study will be coded using the MedDRA coding dictionary.

[figure not shown]
All AEs (serious and non-serious) reported during the course of this study from the first day of study treatment through and including 999 calendar days after the last administration of the study drug will be considered treatment emergent AEs (TEAEs). Only AEs captured in this study will be included, and not AEs captured in the 1-year open label safety study.

A 3-tier approach will be used to summarize AEs. Under this approach, AEs are classified into 1 of 3 tiers. Different analyses will be performed for different tiers (See [Section 8.2.3.1](#)).

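### Protocol 8.2 starts CRF recording of adverse events at the first dose, against the Schedule and visit instructions, and the SAP's day-based window misclassifies Day 1 events that precede the dose

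*Protocol*

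**What the plan says.** Protocol Section 8.2 sets two start points. For the CRF, "AEs (serious and non-serious) should be recorded on the CRF from the time the subject has taken at least one dose of study treatment", continuing to the last visit. For SAE notification to the sponsor, "For serious adverse events, the active reporting period to Pfizer or its designated representative begins from the time that the subject provides informed consent", that is, before any study procedure.

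Other parts of the protocol ask for AEs before the first dose:

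- The Schedule of Activities has its first AE mark under Visit 2 (Day -3 to -1) and none under Visit 1. Section 6.1.1 repeats the instruction for Visit 2: "Assess and record adverse events".
- Section 6.2.1 (Visit 3) lists AE assessment and the brief physical and neurological examinations ahead of the item "Administer first dose of study medication in clinic".
- Section 7.6 says that "Any clinically significant changes from the entry examination will be recorded as adverse events", and has the brief Visit 3 examination document significant changes.
- Section 8.11.2 says that "All adverse events will be reported on the adverse event page(s) of the CRF" and gives no first-dose limit.

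SAP Section 6.2.1, repeated in 8.2.3.1, counts as treatment-emergent all AEs "reported during the course of this study from the first day of study treatment" onward. It does not divide the first day at the dose and has no worsening criterion.

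**The concern.** Sites are given incompatible rules on when CRF recording of AEs begins. A site that follows 8.2 literally leaves a Visit 2 event off the CRF. A site that follows the Schedule and 8.11.2 enters it. Whether a pre-dose event appears in the trial data then depends on which section the site read.

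Two consequences follow. First, the CRF may lack events that began between Visit 1 and the first dose, so one that continues into treatment could be mistaken for new. A pre-dose SAE could sit on the sponsor's SAE form without a matching CRF AE page, although 8.11.2 wants the two forms consistent where they collect the same data. Second, because the SAP window opens on a calendar day and not at the dose, an event that cannot be due to study drug can enter the treatment-emergent count.

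**Working it through.** No figure in the plan is in dispute, so the check sets the texts side by side and traces single events through them.

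**Start of AE capture, by source**

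| Source | Start point | Before first dose? |
|---|---|---|
| Protocol 8.2, CRF recording | First dose | No |
| Protocol 8.2, SAE reporting to sponsor | Informed consent | Yes |
| Schedule and 6.1.1 | Visit 2, Day -3 to -1 | Yes |
| 6.2.1 with 7.6 | Visit 3, listed ahead of the dose | Yes |
| 8.11.2 | No limit stated | Not excluded |
| SAP 6.2.1 and 8.2.3.1, treatment-emergent | First day of treatment | Includes the pre-dose part of that day |

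**Case A: non-serious event at Visit 2.** The Schedule and 6.1.1 say to record it, and 8.11.2 puts it on the CRF. Under 8.2 it is outside the CRF period. It is not treatment-emergent under either rule, because it predates the first treatment day. The divergence is in whether the CRF holds it at all.

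**Case B: serious event at Visit 2.** It goes to the sponsor under the consent start in 8.2. Its CRF entry is expected under 8.11.2 and excluded by the first-dose start in 8.2.

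**Case C: examination change found on Day 1 before dosing.** Sections 6.2.1 and 7.6 make it an AE. At a site that follows the Schedule it is entered with a Day 1 date, and the SAP counts it as treatment-emergent. At a site that follows 8.2 it is not entered and not counted.

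**Case D: event that begins after Visit 1 and continues past the first dose.** Medical history is taken at Visit 1, so it predates the event. Section 8.2 does not assure an AE entry with the true onset. If the event is first entered after dosing without that onset, it looks new.

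**Length of the conflict.** Because the Schedule has no AE mark at Visit 1, the clash with scheduled AE assessments begins at Day -3. That is Days -3, -2 and -1, plus the pre-dose part of Day 1. Divergence in treatment-emergent counts is narrower: only the hours of Day 1 before a dose given in clinic.

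**Direction.** Study drug cannot affect an event before the first dose, so such events have the same expected proportion in each arm. Section 5.1 also stratifies randomization by site, which spreads site recording habits across arms. In expectation the misclassified events raise each arm's rate about equally and largely cancel in the Tier 2 risk differences of SAP 8.2.3.1.

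**The case against.** The best defence is that the protocol is coherent if 8.2 governs. Section 8.1 says AEs are reported as the later sections describe, so 8.11.2 can be read inside the 8.2 window. Section 8.3 defines an AE in a subject who has been administered a product or device, which arguably leaves out screening. Recording at Visits 2 and 3 could then mean source documents only. This weakens 8.11.2 as support, but it does not explain why the Schedule and 6.1.1 call for AE recording at a visit where, on that reading, no AE could be recorded on the CRF. Nor does it touch the SAP window.

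Several stronger readings are tempting, and the documents do not support them:

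- A reader might infer that harms of screening procedures are lost. SAEs go to the sponsor from consent, and events assessed at Visits 2 and 3 may be in source documents. Only non-serious pre-dose events and the CRF copy of pre-dose SAEs are exposed.
- A reader might infer that treatment-emergent events have no pre-dose reference. Medical history, full examinations, laboratory tests and concomitant medications are collected at Visit 1. Brief examinations, vital signs and laboratory tests are listed before the dose at Visit 3. SAP 8.2.3 sets the safety baseline at Visit 3 or the last observation before treatment.
- A reader might cite Section 8.8, where "the investigator must record this causal relationship in the source documents and CRF", as requiring pre-dose recording. That sentence concerns the causality of procedure-related SAEs, is qualified by what is appropriate, and states no timing.
- A reader might size the gap by the whole stretch from screening to dosing, or by the blood drawn in it. The Schedule asks for no AE assessment at Visit 1, and blood volume does not measure unrecorded events.
- A reader might infer that SAE tables or interim reviews will miss pre-dose SAEs. The documents do not say whether those outputs use CRF data or the safety database, and the interim procedures are left to a separate charter.

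**Conclusion.** The contradiction on the CRF start point stands, and so does the SAP's inclusion of Day 1 events that precede the dose. Both are minor. The first affects completeness of the CRF for non-serious pre-dose events and CRF agreement for pre-dose SAEs. The second affects absolute treatment-emergent rates by whatever events fall in the pre-dose hours of Day 1. The documents give no rate from which to put a number on this. Risk differences should be little affected, and SAP 8.2.3 plans no inferential safety analysis.

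This rests on three assumptions: that some sites follow 8.2 literally and others the Schedule, that the SAP window is applied by calendar date as written, and that the Visit 3 assessments are done in the order listed, ahead of the dose.

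**What to change.** Protocol: reconcile 8.2 with the Schedule and Sections 6.1.1, 6.2.1, 7.6 and 8.11.2 by stating one start point for CRF recording of AEs, no later than Visit 2, as the Schedule already requires. Starting at consent would match the SAE notification period but is optional. It would be new for the CRF, because 8.2 now keeps pre-dose SAEs off it as well. For Day 1 events, record whether onset was before or after the first dose.

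SAP 6.2.1 and 8.2.3.1: define treatment-emergent as onset after the first dose, or worsening after it of an event already present, and list pre-dose events separately.

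The cost is a few sentences in the two documents, a change to CRF completion guidance with one added Day 1 item, and slightly more data entry for events that sites are already told to assess.

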8.3. Definition of an Adverse Event

An adverse event is any untoward medical occurrence in a clinical investigation subject administered a product or medical device; the event need not necessarily have a causal relationship with the treatment or usage. Examples of adverse events include but are not limited to:

- Abnormal test findings;
- Clinically significant symptoms and signs;
- Changes in physical examination findings;
- Hypersensitivity;
- Progression/worsening of underlying disease;
- Drug abuse;

- Drug dependency.

Additionally, they may include the signs or symptoms resulting from:

- Drug overdose;
- Drug withdrawal;
- Drug misuse;
- Drug interactions;
- Extravasation;
- Exposure during pregnancy;
- Exposure via breastfeeding;
- Medication error;
- Occupational exposure.

8.4. Abnormal Test Findings

The criteria for determining whether an abnormal objective test finding should be reported as an adverse event are as follows:

- Test result is associated with accompanying symptoms, and/or
- Test result requires additional diagnostic testing or medical/surgical intervention, and/or
- Test result leads to a change in study dosing (outside of protocol-stipulated dose adjustments) or discontinuation from the study, significant additional concomitant drug treatment, or other therapy, and/or
- Test result is considered to be an adverse event by the investigator or sponsor.

Merely repeating an abnormal test, in the absence of any of the above conditions, does not constitute an adverse event. Any abnormal test result that is determined to be an error does not require reporting as an adverse event.

8.5. Serious Adverse Events

A serious adverse event is any untoward medical occurrence at any dose that:

- Results in death;

- Is life-threatening (immediate risk of death);
- Requires in subject hospitalization or prolongation of existing hospitalization;
- Results in persistent or significant disability/incapacity (substantial disruption of the ability to conduct normal life functions);
- Results in congenital anomaly/birth defect;

Medical and scientific judgment is exercised in determining whether an event is an important medical event. An important medical event may not be immediately life-threatening and/or result in death or hospitalization. However, if it is determined that the event may jeopardize the subject, or may require intervention to prevent one of the other adverse event outcomes, the important medical event should be reported as serious.

Examples of such events are intensive treatment in an emergency room or at home for allergic bronchospasm; blood dyscrasias or convulsions that do not result in hospitalization; or development of drug dependency or drug abuse.

8.5.1. Protocol-Specified Serious Adverse Events

There are no protocol-specified SAEs in this study. All SAEs will be reported by the investigator as described in previous sections, and will be handled as SAEs in the safety database (see Section on [Serious Adverse Event Reporting Requirements](#))

8.5.2. Potential Cases of Drug-Induced Liver Injury

Abnormal values in aspartate transaminase (AST) and/or alanine transaminase (ALT) concurrent with abnormal elevations in total bilirubin that meet the criteria outlined below in the absence of other causes of liver injury are considered potential cases of drug-induced liver injury (potential Hy's Law cases) and should always be considered important medical events.

The threshold of laboratory abnormalities for a potential case of drug-induced liver injury depends on the subject's individual baseline values and underlying conditions. Subjects who present with the following laboratory abnormalities should be evaluated further to definitively determine the etiology of the abnormal laboratory values:

- Subjects with AST or ALT and total bilirubin baseline values within the normal range who subsequently present with AST or ALT ≥ 3 times the upper limit of normal (X ULN) concurrent with a total bilirubin ≥ 2 X ULN with no evidence of hemolysis and an alkaline phosphatase ≤ 2 X ULN or not available.
- For subjects with preexisting ALT OR AST OR total bilirubin values above the upper limit of normal, the following threshold values should be used in the definition mentioned above:

- For subjects with pre-existing AST or ALT baseline values above the normal range: AST or ALT ≥ 2 times the baseline values and ≥ 3 X ULN, or ≥ 8 X ULN (whichever is smaller).
- **Concurrent with**
 - For subjects with pre-existing values of total bilirubin above the normal range: Total bilirubin increased by one time the upper limit of normal **or** ≥ 3 times the upper limit of normal (whichever is smaller).

The subject should return to the investigational site and be evaluated as soon as possible, preferably within 48 hours from awareness of the abnormal results. This evaluation should include laboratory tests, detailed history and physical assessment. In addition to repeating AST and ALT, laboratory tests should include albumin, creatine kinase, total bilirubin, direct and indirect bilirubin, gamma-glutamyl transferase (GGT), prothrombin time (PT)/INR, and alkaline phosphatase. A detailed history, including relevant information, such as review of ethanol, acetaminophen, recreational drug and supplement consumption, family history, occupational exposure, sexual history, travel history, history of contact with a jaundiced subject, surgery, blood transfusion, history of liver or allergic disease, and work exposure, should be collected. Further testing for acute hepatitis A, B, or C infection and liver imaging (eg, biliary tract) may be warranted. All cases confirmed on repeat testing as meeting the laboratory criteria defined above, with no other cause for liver function test (LFT) abnormalities identified at the time should be considered potential Hy's Law cases irrespective of availability of all the results of the investigations performed to determine etiology of the abnormal LFTs. Such potential Hy's Law cases should be reported as serious adverse events.

8.6. Hospitalization

Adverse events reported from studies associated with hospitalization or prolongations of hospitalization are considered serious. Any initial admission (even if less than 24 hours) to a healthcare facility meets these criteria. Admission also includes transfer within the hospital to an acute/intensive care unit (eg, from the psychiatric wing to a medical floor, medical floor to a coronary care unit, neurological floor to a tuberculosis unit).

Hospitalization does not include the following:

- Rehabilitation facilities;
- Hospice facilities;
- Respite care (eg, caregiver relief);
- Skilled nursing facilities;
- Nursing homes;

- Routine emergency room admissions;
- Same day surgeries (as outpatient/same day/ambulatory procedures).

Hospitalization or prolongation of hospitalization in the absence of a precipitating, clinical adverse event is not in itself a serious adverse event. Examples include:

- Admission for treatment of a preexisting condition not associated with the development of a new adverse event or with a worsening of the preexisting condition (eg, for work-up of persistent pre-treatment lab abnormality);
- Social admission (eg, subject has no place to sleep);
- Administrative admission (eg, for yearly physical exam);
- Protocol-specified admission during a study (eg, for a procedure required by the study protocol);
- Optional admission not associated with a precipitating clinical adverse event (eg, for elective cosmetic surgery);
- Hospitalization for observation without a medical AE;
- Pre-planned treatments or surgical procedures should be noted in the baseline documentation for the entire protocol and/or for the individual subject.

Diagnostic and therapeutic non-invasive and invasive procedures, such as surgery, should not be reported as adverse events. However, the medical condition for which the procedure was performed should be reported if it meets the definition of an adverse event. For example, an acute appendicitis that begins during the adverse event reporting period should be reported as the adverse event, and the resulting appendectomy should be recorded as treatment of the adverse event.

